4 STUDY DESIGN

This randomized, multicenter (ie, approximately 200 global centers), open-label, non-inferiority Phase 3 study is designed to evaluate the efficacy and safety of acalabrutinib versus ibrutinib in subjects with relapsed or refractory CLL who have high-risk prognostic markers (eg, 17p del and/or 11q del) per NCCN guidelines ([NCCN Version 1.2016](#)).

Figure 4-1. Study Schema

Approximately 500 eligible subjects will be randomized in a 1:1 ratio into 2 arms to receive either acalabrutinib 100 mg BID (Arm A; N=250) or ibrutinib 420 mg QD (Arm B; N=250).

This study will use an IWRS for randomization. Randomization will be used to minimize bias in the assignment of subjects to treatment groups, to increase the likelihood that known and unknown subject attributes (eg, demographic and baseline characteristics) are evenly balanced, and to enhance the validity of statistical comparisons across treatment groups.

Randomization will be performed stratified by the following factors:

- Presence of 17p del
- ECOG performance status (ECOG = 2 versus ECOG \leq 1)
- Number of prior therapies (1-3 versus \geq 4)

Subject participation will include a Screening Phase, a Treatment Phase, a Post-treatment Phase, and a Post-disease Progression Phase. The Screening Phase will last up to 28 days before first dose of study drug, during which the subject's eligibility and baseline characteristics will be determined. The Treatment Phase will last from randomization until study drug discontinuation. Subjects will receive study drug daily until disease progression or unacceptable toxicity. The Post-treatment Phase will follow subjects for disease progression or death, if they

discontinued study drug treatment due to unacceptable toxicity or any reason. Subjects who withdraw consent or are lost to follow will not be followed for disease progression or survival.

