7.2.2.1 Adverse Event Reporting Period

After the signing of the ICF and prior to the first dose of study drug, all SAEs must be reported.

After the first dose of study drug, all AEs/SAEs, irrespective of attribution of causality, must be reported.

All adverse events will be reported until 30 days after the last dose of study drug or the start of new anticancer therapy (whichever comes first). After this period, investigators should report serious adverse events or other adverse events of concern that are believed to be related to prior treatment with study drug.

All SAEs that occur during the reporting period should be followed to resolution or until the Investigator assesses the subject as stable or until the subject is lost to follow up or withdraws consent. Resolution/stable means the subject has returned to baseline state of health or the Investigator does not expect any further improvement or worsening of the event.

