#### **4.2.1 Adverse Events, Concomitant Medications, Prior/Subsequent Anticancer Therapies, Initial Diagnosis**

Imputation of partial dates will be made for AE onset and stop dates, start and end dates of concomitant medication, start date of prior/subsequent anticancer therapy, and date of initial diagnosis. If dates are completely missing, no imputation will be made. For any partial date with missing year, no imputation will be made.

The general rule for imputation is:

- If only day is missing, then the 15th of the month will be used.
- If only year is present, then June 30th will be used.

If such imputed date for initial diagnosis or prior anticancer therapy is on or after date of randomization, then date of randomization – 1 will be used. If such imputed date for

subsequent anticancer therapy is before date of last dose, then date of last dose + 1 will be used.

If the imputed date is for an AE start date and is in the same year and month as but before the first dose date, then the first dose date will be used, or if the imputed AE start date is after the AE end date, then the AE end date will be used. If the imputed date is for an AE start date and is in the same year and month as but after the last dose date + 30 days, then the last dose date + 30 days will be used.

If the imputed date is for an AE end date and is after the death date, then the death date will be used, or if the imputed AE end date is before the AE start date, then the AE start date will be used.

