## **7.2 Secondary Endpoints and Analyses**

### **7.2.1 Grade $\geq 3$ Infections, Richter's Transformation, and Atrial Fibrillation**

Secondary endpoints related to safety will be analyzed using the safety population, and subjects will be analyzed as treated. If a subject incorrectly received both acalabrutinib and ibrutinib in any amount, the subject will be analyzed under the acalabrutinib arm.

The incidences of treatment emergent grade  $\geq 3$  infections, Richter's transformation, and atrial fibrillation will be summarized and compared between the 2 treatment arms using 2-sided Cochran-Mantel-Haenszel tests adjusted for the randomization strata (same strata used for the primary analysis of PFS based on the pre-specified pooling strategy).

Richter's transformation will be assessed by central pathology. Incidence of grade  $\geq 3$  infections and atrial fibrillation will be collected as described for all AEs and defined according to Appendix 1.

In addition, subgroup analyses will be performed for each endpoint using the subgroups listed in Section 7.1.4. For each endpoint, the risk difference (Arm A – Arm B) and its

corresponding 95% CI for each subgroup will be calculated based on normal approximation (with use of Wilson's score) and displayed graphically in a forest plot.

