### **8.1.1 Treatment Emergent Adverse Events**

TEAE is defined as an adverse event reported during the treatment emergent period (defined in Section 4.1.6). Any ongoing event that worsens in severity after the first dose date of study drug is also defined as a TEAE. Incomplete onset dates will be imputed as detailed in Section 4.2, for the purpose of determining whether AEs are treatment emergent.

TEAEs will be tabulated in summary tables by treatment arm. For each treatment arm, frequency and percentage of adverse events within each system organ class and preferred term will be presented. The denominator for the adverse event incidence will be based on the number of safety population subjects in that treatment arm, unless otherwise specified. Adverse event incidence rates will also be summarized by severity and relationship to study drug based on the investigator’s judgment.

Subjects with multiple occurrences of events for a given preferred term, system organ class, or overall will be counted only once at the maximum severity and strongest relationship to study drug, respectively, for each preferred term and system organ class.

In addition, Grade 3 or Grade 4 TEAEs, TEAEs that led to permanent study drug discontinuation, TEAEs that led to dose reduction, TEAEs that led to dose interruption, serious TEAEs, and TEAEs that resulted in death will be summarized by treatment arm as treated.

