### **8.1.2 Adverse Events of Clinical Interest**

Adverse events of clinical interest (ECIs) are specified in Appendix 1 and are to be reported for the duration of study treatment and during any protocol-specified follow-up periods, including post-disease progression phase for overall survival. These events will be summarized similarly to TEAEs by treatment arm.

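### SAP 4.2.1 dates an AE recorded only with the calendar year of first dose as pre-treatment when first dose fell from July 1 to December 31 (not treatment-emergent unless it later worsens); separately, SAP 4.2.2 censors a death known only by year.

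*SAP*

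**What the plan says.** **AE onset.** The general rule in SAP 4.2.1 for a date without day and month is "If only year is present, then June 30". For an AE start there is one forward correction: if the imputed date "is in the same year and month as but before the first dose date, then the first dose date will be used". The other two corrections to an AE start can only move it back, to the AE end date or to 30 days after last dose. SAP 4.1.6 starts the treatment-emergent period at first dose, and SAP 8.1.1 ties the two together: "Incomplete onset dates will be imputed as detailed in Section 4.2, for the purpose of determining whether AEs are treatment emergent". SAP 8.1.1 also gives a second route to treatment-emergent status: "Any ongoing event that worsens in severity after the first dose date of study drug is also defined as a TEAE".

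Protocol 9.5 says that partial AE dates will be imputed by prespecified, conservative rules.

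**Death.** SAP 4.2.2 imputes a death date that lacks only the day. If the month is missing too, or the whole date is missing, nothing is imputed and survival time is censored. SAP 7.2.2 applies right-censoring to subjects who are not known to have died by the data cutoff.

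**The concern.** The forward correction appears meant to keep a probable on-treatment AE from being dated before treatment by the imputation itself. It requires the imputed onset and first dose to share a month, and a June 30 date cannot meet that condition while also preceding first dose. The protection is therefore absent where the date is least certain.

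The AE form makes a post-dose onset the more likely one. Protocol 7.2.2.1 says "After the signing of the ICF and prior to the first dose of study drug, all SAEs must be reported", and requires all AEs only after first dose. Protocol 4 limits the earlier period: "The Screening Phase will last up to 28 days before first dose of study drug". A non-serious AE on the form most likely began on or after first dose. Dating it before first dose removes it from the TEAE tables, which is hard to call conservative for safety.

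Two formally tested endpoints use the same classification. Under SAP 7.2.1 the treatment-emergent incidence of "atrial fibrillation will be summarized and compared between the 2 treatment arms", as is that of Grade 3 or higher infections. SAP 2.6 places them first and second in the fixed sequence, with OS fourth. For OS, SAP 4.2.2 and 7.2.2 disagree on whether a known death counts.

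**Working it through.** The plan states no figure that depends on these rules, so there is nothing to reproduce. The check applies SAP 4.2.1 as written to every first-dose day of a 365-day year.

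**1. When the forward correction acts.**

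- *Year only, same calendar year as first dose.* The imputed onset is June 30. For a June first dose it is never earlier than first dose; for any other month the same-month condition fails. The correction acts on 0 of 365 first-dose days.
- *Resulting onset.* For first doses from January 1 to June 30 (181 days), June 30 is on or after first dose. For July 1 to December 31 it is before: 31 + 31 + 30 + 31 + 30 + 31 = 184 days, or 184/365 = 50.4%.
- *Year only, a later year than first dose.* June 30 of a later year follows first dose: 0 days misdated as pre-dose.
- *Day missing, month of first dose.* The 15th is imputed. The correction acts on 185 of 365 days (first dose on the 16th or later) and leaves 0 pre-dose.

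The sentence therefore works for the case it seems to have been written for and fails only for year-only dates.

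**2. Share of year-only records affected.** Assumptions, none of them from the documents: first-dose dates uniform over the year, and a true onset on or after first dose in the same calendar year.

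- *Constant AE rate to December 31.* All pairs of first-dose day and onset day: 365 × 366 / 2 = 66,795. Pairs with first dose from July 1: 184 × 185 / 2 = 17,020. Share: 17,020 / 66,795 = 25.5%.
- *Onsets only in the first 84 days (12 weeks).* All pairs: 282 × 84 + (83 × 84 / 2) = 23,688 + 3,486 = 27,174. First dose from July 1: 101 × 84 + 3,486 = 11,970. Share: 11,970 / 27,174 = 44.0%.
- *Range.* 0% if every first dose fell in January to June; 100% if every one fell in July to December.

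**3. Opposite direction.** For true onsets in the 28 days before first dose, in the same year, all pairs are 378 + 337 × 28 = 9,814. Those with first dose by June 30 are 378 + 153 × 28 = 4,662. So 4,662 / 9,814 = 47.5% of such year-only onsets become treatment-emergent. Only SAEs must be reported in that period, so few records should arise there.

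**4. Scale.** One subject lost from an incidence is 1/250 = 0.4 percentage points of a planned arm.

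**5. Death.** Take a subject whose recorded death year is earlier than the cutoff year.

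| Section | Result for this subject |
|---|---|
| SAP 7.2.2 | Known to have died before cutoff, so outside the group to be right-censored |
| SAP 4.2.2 | Month and day missing, so survival time is censored |

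The two results differ for the same subject. If the death were dated at January 1 of its year, the largest error would be January 1 to December 31, which is 364 days (365 in a leap year). If the roughly 12-weekly survival contact in Protocol 7.1 was kept after progression, dating the death on the day after last known alive would limit the error to about 12 × 7 = 84 days.

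**The case against.** The strongest reply is that the records may not exist. In the treatment phase, visits are weekly for 8 weeks and then every 4 weeks to Week 24, AEs are recorded with start and end dates, SAEs are due within 24 hours of discovery, and data are cleaned before lock. Year-only onsets are least plausible just after first dose, which is the case behind the 44.0% figure. This stands: the percentages are shares of year-only records, not of all AEs, and the documents give no count of such records.

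A second reply is that a post-dose onset is less certain for the tested endpoints. A Grade 3 or higher infection may be an SAE through hospitalization, and SAEs are reportable before first dose. This also stands in part, and the proposed text therefore excepts documented pre-dose SAEs.

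On deaths, SAP 4.2.2 is an explicit, prespecified rule, and Table 3 needs a date of death for an event, so 4.2.2 can be read as a specific supplement to 7.2.2. Death dates must be documented for every randomized subject (Protocol 4), and SAP 8.2 lists all deaths, so a censored death stays visible. That limits the consequence, but a known death would still not count in a tested endpoint.

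A reader might also infer more than the documents support:

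- *That the cut-off at 30 days after last dose is equally faulty.* SAP 8.1.2 expects events of clinical interest to be "reported for the duration of study treatment and during any protocol-specified follow-up periods, including post-disease progression phase for overall survival", so an onset after the window can be genuine. That side is a trade-off and no error is shown.
- *That SAP 4.2.3 contradicts 4.2.2 because it imputes January 1 for a year-only date last known alive.* That date is a lower bound on a censoring time; it does not commit the plan to creating an event date.

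**Conclusion.** Both points hold on the text, as minor drafting faults.

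An AE is wrongly made pre-treatment only when its onset has a year alone, that year is the calendar year of first dose, first dose was July 1 to December 31, the true onset was on or after first dose, and the event does not later worsen. Under the stated assumptions this is 25.5% to 44.0% of year-only onsets truly on or after first dose in that calendar year. A subject with another properly dated qualifying event is not lost.

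It would be wrong to infer that every year-only AE in a subject first dosed in the second half of a year is lost, since later-year onsets are unaffected. Nor do the documents support bias toward one arm or a power effect: first-dose dates should be similar across randomized arms, the June 30 rule can also move pre-dose onsets into the window, and the number of records is unknown and probably very small. The likely effect is a little lost information.

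The death point covers deaths whose recorded year precedes the cutoff year. For a wholly missing date, or a year-only death in the cutoff year, death by cutoff may not be known, and the present rule is defensible.

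**What to change.** **SAP 4.2.1.** Replace the first-dose clause with: *If the recorded part of an AE start date is compatible with onset on or after first dose and the imputed date is before first dose, the first dose date will be used, unless the AE end date precedes first dose or the record is an SAE documented as before first dose.* With this text, 0 of the 66,795 pairs in step 2 are misclassified. Leave the rule at 30 days after last dose unchanged.

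**SAP 4.2.2.** Count a death whose recorded year is before the cutoff year as an OS event, dated at the later of January 1 of that year and the day after last known alive. Treat a death year earlier than the year of last contact as a data error to query. Keep the present rule for wholly missing dates and for year-only deaths in the cutoff year, unless other records establish death by cutoff. Report the present censoring rule as an OS sensitivity analysis, and cross-refer 4.2.2 and 7.2.2.

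**Cost.** A short text change in each of two subsections, a date-macro edit and one OS sensitivity run, preferably settled before unblinding. The downsides are that a pre-dose SAE with a year-only onset and no pre-dose documentation could be counted as treatment-emergent, and that a few deaths would carry an approximate date, at most about one year early.

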#### **4.2.2 Death Dates**

If death year and month are available but day is missing:

- If mmyyyy for last contact date = mmyyyy for death date, set death date to the day after the last contact date.
- If mmyyyy for last contact date < mmyyyy for death date, set death date to the first day of the death month.
- If mmyyyy for last contact date > mmyyyy for death date, data error and do not impute.

If both month and day are missing for death date or a death date is totally missing, do not impute and censor the subject survival time.

#### **4.2.3 Date Last Known Alive**

If year and month of date last known alive are available but day is missing, set date to the 1st of the month.

If both month and day are missing, set date to January 1st of the year.

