### 7.2.2 Overall Survival

OS will be analyzed using the ITT population and is defined as the time from date of randomization to date of death due to any cause. Subjects who were not known to have died prior to the analysis data cutoff date will be right-censored as follows:

**Table 3.** Overall Survival Censoring

Situation	Date of Event or Censoring	Outcome
Death before first disease assessment	Date of death	Event
Death between scheduled assessments	Date of death	Event
All other cases will be censored as follows:		
Lost to follow-up immediately after randomization	Randomization date	Censored
Not known to have died at or prior to analysis data cutoff date	Date last known alive before analysis data cutoff date	Censored
Not known to have died prior to lost to follow-up or study exit	Date last known alive before lost to follow-up or study exit	Censored

OS will be calculated as death date (or censoring date) - randomization date + 1.

OS will be analyzed in the same fashion as that for primary efficacy endpoint as described in Section 7.1.2. A stratified log rank test will be performed, adjusting for the randomization stratification factors used for the primary analysis.

Additionally, a subgroup analysis will be performed for OS in the same manner, and using the same subgroups, as described in Section 7.1.4.

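### The imputed date last known alive has no lower bound, so a partial date can give a zero or negative overall survival time; the handling of survivors at the data cutoff could also be stated more exactly

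*SAP*

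**What the plan says.** **Partial dates.** SAP 4.2.3 has two rules for the date last known alive. The first is "If year and month of date last known alive are available but day is missing, set date to the" 1st of the month. The second is "If both month and day are missing, set date to January" 1st of the year. Nothing further is said, and the SAP does not define how the date is derived from visits, scans, laboratory samples and contacts.

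**Other imputed dates.** SAP 4.2.1 adds checks for several dates. For an imputed date of new therapy, if "subsequent anticancer therapy is before date of last dose, then date of last dose + 1 will be used". Adverse event start and end dates are checked against dosing, death and each other. Prior-therapy and diagnosis dates are held before randomization. In SAP 4.2.2, a partial death date in the same month as the last contact follows this rule: "set death date to the day after the last contact date".

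**OS.** SAP 7.2.2 states: "OS will be calculated as death date (or censoring date) - randomization date + 1". Table 3 counts deaths up to the cutoff as events. A subject described as "Not known to have died at or prior to analysis data cutoff date" is censored at "Date last known alive before analysis data cutoff date". The randomization date is the censoring date in one row only: "Lost to follow-up immediately after randomization".

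**Data used.** SAP 2.5 restricts the final analysis to data available up to the cutoff. Protocol 7.1 plans survival contacts about every 12 weeks after progression, and a survival sweep at study closure.

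**The concern.** An OS time below zero is impossible. A subject with such a time cannot contribute properly to the Kaplan-Meier curve, the log-rank test or the Cox model. The subject would be dropped from an analysis defined on all randomized subjects, or the date would be repaired by a rule chosen after the SAP was final. SAP 2.6 places OS in the gate-kept sequence, so its derivation should leave no such choice open.

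A second, smaller matter concerns the cutoff. If a contact after the cutoff shows that a subject was alive on that day, Table 3 as worded still censors at an earlier contact, whereas a death in the same gap counts. Events in the last interval are then counted without all of the matching time at risk, which pulls the late survival estimate slightly down.

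**Working it through.** **Plan's own figure.** The documents give no OS event count or OS power, so there is no OS figure to reproduce. The design figure that can be checked is the roughly 250 PFS events (Protocol 9.3). With margin 1.429, two-sided alpha 0.05, 80% power and 1:1 allocation, 4 x (1.960 + 0.842)^2 / (ln 1.429)^2 gives 247 after rounding up, so the figure reproduces. It has no bearing on this point.

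**Step 1: when the OS time fails.** Suppose the recorded partial date falls in the month of randomization (day missing) or the year of randomization (day and month missing).

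- Day missing, randomized on day d of the month: OS = 1 - d + 1 = 2 - d. This is zero for d = 2 and negative for d of 3 or more.
- Day and month missing, randomized on day y of the year: OS = 1 - y + 1 = 2 - y.

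Example with an assumed randomization date of 20 March 2016, which is day 80 of that year:

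- March 2016 recorded: 2 - 20 = -18 days.
- Only 2016 recorded: 2 - 80 = -78 days.

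**Step 2: size of the shift.** Over every calendar date from 2016 to 2020, moving back to the 1st of the month shifts the date by 14.7 days on average (maximum 30). Moving back to 1 January shifts it by 182 days on average (maximum 365, in a leap year). A conflict with a complete alive date needs that date to lie in the same month, or for a year-only date in the same year, as the partial one.

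**Step 3: does anything else act as a floor?** The checks in SAP 4.2.1 and 4.2.2 apply to other dates. The randomization-date row of Table 3 covers only immediate loss to follow-up. So no general floor exists.

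**Step 4: the cutoff rule.** A simulation compared Table 3 read literally (survivors censored at the last scheduled contact before the cutoff) with censoring survivors at the cutoff. Assumptions, none of them from the documents: uniform accrual over 24 months, cutoff at month 60, exponential survival, true HR 1, and every survivor contacted after the cutoff. It used 500 subjects, as planned, and 300 replicates per scenario.

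| 48-month mortality | Contact interval | KM mortality, cutoff / literal | Death rate, literal / cutoff | HR, cutoff / literal |
|---|---|---|---|---|
| 20% | 12 weeks | 20.12% / 20.55% | 1.026 | 1.009 / 1.009 |
| 30% | 12 weeks | 30.12% / 30.71% | 1.024 | 1.005 / 1.005 |
| 20% | 24 weeks | 20.02% / 21.07% | 1.056 | 0.978 / 0.978 |
| 30% | 24 weeks | 30.18% / 31.62% | 1.052 | 0.991 / 0.991 |
| 20% | 12 weeks in one arm, 24 in the other | 19.72% / 20.41% | 1.041 | 1.005 / 1.049 |

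With 12-week contacts, 48-month mortality is overstated by about 0.4 to 0.6 points. With 24-week contacts the figure is about 1.1 to 1.4 points. Within each scenario with equal schedules the HR is the same under both rules. It moves only in the last row, an extreme case, because the schedule in Protocol Appendix A is common to both arms.

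**The case against.** The strongest reply is that the imputation is conservative by design. The start of the month or year credits no survival that was not observed. That stands: the default is sound, and the defect is only that it is not bounded below.

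The failing case is also narrow. A negative time needs a subject whose last evidence of life is a partial date in the month or year of randomization. The documents do not say how common partial dates are, so a loss of randomized subjects from the OS analysis is a possibility and not an expected effect. That stands too.

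A reader might infer that the SAP discards dated evidence, so that a subject with a complete visit in October 2019 and a last-known-alive year of 2019 is necessarily censored on 1 January 2019. The documents do not support this. It assumes a single recorded field that overrides complete visit dates. In its ordinary sense, the date last known alive is the latest evidence of life, and a complete October visit could itself be that date. What can be said is that the derivation is undefined and that nothing prevents this result.

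A reader might also infer a large loss of follow-up at the cutoff. The documents give neither the number of survivors nor the share with a later contact, so no total of lost patient-years can be supported. Table 3 is consistent with SAP 2.5, under which contacts after the cutoff lie outside the analysis data, and a programmer could still cap at the cutoff. This part therefore rests on a literal reading, and changing Table 3 alone would leave it at odds with SAP 2.5.

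**Conclusion.** The missing floor in SAP 4.2.3 is a real defect. Applied as written with the formula in SAP 7.2.2, the rule can return impossible OS times, such as -18 or -78 days in the illustrative case. It is minor: it arises only for partial dates, whose frequency is unknown. Both arms share the rule, so the effect on the OS hazard ratio should be small unless partial dates differ by arm.

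The cutoff wording is a secondary improvement and not an error of the same kind. Under the assumptions listed, it changes late Kaplan-Meier mortality by about half a percentage point with 12-week contacts and leaves the hazard ratio where it was when both arms share a schedule.

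That OS is gate-kept might suggest that a formal conclusion is at risk. The documents do not support that: OS is fourth and last in the sequence, and no test decision has been shown to change.

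**What to change.** **SAP 4.2.3, main change.** Add: *Use the later of the imputed date, the randomization date and the latest complete date on which the subject is documented alive.* List the sources of complete dates (at least visits, scans, laboratory samples, dosing and survival contacts), so that the derivation is defined.

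**SAP 7.2.2, Table 3, secondary change.** Add a row: *A subject known to be alive, or to have died, after the data cutoff is censored at the cutoff.*

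**SAP 2.5.** Add that survival status obtained after the cutoff may be used for this purpose only. Without this, the new row in Table 3 would conflict with the restriction to data up to the cutoff.

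The cost is a few sentences in the SAP and a small change to the OS derivation program, best made before unblinding. No hypothesis, significance level, sample size or data collection changes.
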